**Table 2: Partial Dates Imputation Rules for Initial Diagnosis and Diagnosis of Disease**

Parameter	Missing	Additional Conditions	Imputation
Initial Diagnosis Date	D	M and Y the same as M and Y of first dose date of study drug	Date of the first day of month of TRTSDT
		M and/or Y not same as first dose date of study drug	Day 15 of the month of diagnosis
	D and M	Y the same as Y of first dose date of study drug(s)	Date of the first day of month of TRTSDT
		Y prior to Y of first dose date of study drug	01 July of the year of diagnosis
	D, M and Y	None	No imputation

- 3) Partial or missing dates for Concomitant Medication
  - If missing the day and/or month of the start date, the medication will not be considered as concomitant if the month and/or year of the start date is after the last dose date + 30 days or (date of initiation of subsequent anti-cancer therapy -1 day), whichever is earlier
  - If missing day and/or month of the stop date, the medication will not be considered as concomitant if the month and/or year of the stop date is prior to C1D1
  - A medication with completely missing start and end dates will be classified as concomitant.
- 4) For death date, the following conventions will be used:
  - If the death date is completely missing but reason for death is present, it will be imputed as the last known alive date

- If the death date is partially missing (missing day only, or missing both day and month), the death date and corresponding last known alive date will be imputed in 2 steps:
  - 1. Imputed as the 1st of the month (missing day only) or January 1st of the year (missing both day and month)
  - 2. The imputed death date from step 1 will be compared to the latest alive date captured from multiple sources (unimputed), and the later of the two will be considered as the imputed death date and last known alive date

## 6.5 Conversion between Day, Month and Year

Conversions between different time unit will be based on days. For conversion to month and year, the following formula are used: month=days/30.4375, year=days/365.25.

Days of duration and time to events are calculated with the following formula:

(later assessment or study treatment [or follow-up] end date) – (earlier assessment or study treatment start date) +1.

## 6.6 Definitions

### Run-in period:

Eligible patients on combination therapy will receive cetuximab 400mg/m^2 IV as a loading dose during the study run-in period (Day -7). The run-in period therefore starts from the time the patient receives cetuximab and ends when the patient receives combination treatment of NKTR-255 +cetuximab.

**Study drug or study treatment:** Study drug or study treatment refers to NKTR-255 or cetuximab.

**Study day:** Study Day 1 (C1D1) is the first day that the combination treatment of NKTR-255 +cetuximab begins.

**Baseline:** Unless otherwise specified, the baseline value for each variable is the last non-missing value collected at the time (if collected) closest to, but prior to, the start of NKTR-255 administration. For triplicate ECG data, the record with three non-missing value will be considered as non-missing. If multiple measurements occur on the same day at the same time, or on the same day but the time is not available, the average of the measurements (for continuous data) will be considered the baseline value. When dosing times and/or observation times are not collected, it is assumed that protocol planned in-office assessments obtained on the day of the first dose of study drug are prior to administration of the first dose of study drug and therefore considered baseline values.

**Last known alive date:** The date of last known alive date will be derived for patients unknown to have died or known alive at the analysis cut-off by using following dates:

- Patient assessment dates (blood draws **CCI** [REDACTED], vital signs, performance status, ECG, tumor assessments, ECOG, or tumor biopsy dates)
- Start and end dates of anti-cancer therapies administered after study treatment discontinuation
- AE start or end date
- Concomitant medication start or end dates
- Last date of contact collected on the 'Survival follow-up' eCRF (do not use date of survival follow-up assessment unless status is 'alive')
- Study treatment start or end date
- Date of discontinuation for study participation on disposition eCRF pages (do not use if reason for discontinuation is lost to follow-up)

Only dates associated with actual examinations of the patient will be used in the derivation. Dates associated with a technical operation unrelated to patient status such as the date a blood sample was processed will not be used.

**End of Study:** End of study is defined as no more than 2 years after the last patient received his or her last dose of NKTR-255 or Sponsor decision to terminate the study, whichever comes first.

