- a. All procedures and examinations should be performed before the administration of study drug(s) on dosing days, except as indicated. The acceptable visit window is + 1 day for Day 1. If scheduled visits or assessments coincide with a weekend or holiday, schedule at the next feasible date. Please contact the Medical Monitor to discuss any concerns about study visits or assessments that may fall out of the protocol-specified window because of unforeseen delays or other patient-specific circumstances. All out-of-window visits and procedures will incur a protocol deviation.
- b. The EOT visit should occur within 7 days after study treatment is discontinued, or before a new antineoplastic regimen has been initiated.
- c. Safety follow-up visit to occur 60 days after the last dose of study treatment. Survival follow-up visits will occur every 3 months from EOT.
- d. Includes previous immunotherapy, chemotherapy, targeted therapy, radiation therapy, prescription medications, over-the-counter medications, and herbal and dietary supplements.
- e. Patients with HNSCC must also have HPV and EBV status at Screening or provide historical assessment results.
- f. Brain MRI is only required for patients with a history of brain metastases. A standard-of-care brain MRI occurring prior to the 28-day screening window may be acceptable based on consultation with the Medical Monitor.
- g. See Section 7.13. Screening and End of Treatment physical examinations will be a complete physical examination. Symptom-directed physical examinations should be performed at the discretion of the Investigator to identify changes from baseline or to evaluate changes based on the patient's clinical symptoms during other clinic visits. The patient's height is measured at the Screening visit.
- h. The dose does not need to be recalculated for weight changes that are < 10% from baseline (Day -7).
- i. Vital signs to be recorded include temperature, pulse, respiration, systolic and diastolic blood pressure, and oxygen saturation (PaO2). PaO2 monitoring is required only at Screening and on dosing days. Collect vital signs before PK sample collection when both vital signs and PK samples are scheduled for the same timepoint, except EOI timepoint. CCI [REDACTED]  
[REDACTED]
- j. An echocardiogram or MUGA or nuclear scan for cardiac function and measurement of LVEF is required prior to dosing and may have been obtained within 60 days prior to C1D1.

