- k. On C1D1 and C2D1, ECGs are required predose and end of NKTR-255 infusion. All other timepoints, collect ECGs predose. Patients must be resting quietly in the supine position for  $\geq$  5 minutes prior to collection of 12-lead ECG.
- l. For women of childbearing potential (WCBP) only, perform a serum beta subunit of human chorionic gonadotropin ( $\beta$ -HCG) pregnancy test at Screening within 10 to 14 days prior to dosing, and urine or serum pregnancy test within 24 hours prior to day of dosing NKTR-255 on C1D1. In subsequent cycles, perform urine or serum test once each dosing cycle. A negative result is required prior to dosing. Pregnancy testing is not required for women who are postmenopausal for at least 1 year, or surgically sterile for at least 3 months prior to signing the ICF.

- m. See [Appendix 4](#). Central safety laboratory results must be used to determine patient eligibility, with the exception that pregnancy tests are done locally (see Section 7.11); thereafter, central laboratory samples must be obtained prior to each cycle. If local laboratory results are used for retreatment decisions due to timing issues (eg, predose, treatment-related AE management, dose delays, etc.), duplicate central safety laboratory tests must be submitted to the central laboratory.
- n. Tests include free or total triiodothyronine (T3) reflex testing if TSH is abnormal.
- o. Refer to the Laboratory Manual for sample processing. See [Table 7](#) for detailed sampling timepoints.

- u. NKTR-255 will be administered q21d starting C1D1.
- v. Cetuximab will be administered at the recommended dose according to the current local prescribing information, ie, IV weekly. A loading dose of 400 mg/m^2 IV is given as an initial dose, then weekly doses of 250 mg/m^2 IV. On days that NKTR-255 and cetuximab are both dosed, cetuximab should be administered first, [CCI](#)
- w. Patients will remain on treatment until meeting one of the criteria for discontinuation of treatment in Section [5.2.3.1](#).

CCI

CCI

CCJ

CCI

CCI

CCI

CCI

CCI

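### The SAP 6.6 baseline fallback makes no exception for planned post-dose assessments, so an untimed end-of-infusion ECG on C1D1 could enter baseline

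*SAP*

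**What the plan says.** SAP 6.6 (Definitions, Baseline) starts with a main rule: baseline is the latest available value "closest to, but prior to, the start of NKTR-255 administration". Two further rules deal with values that clock time cannot order.

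- Averaging: if several values fall "on the same day but the time is not available, the average of the measurements (for continuous data) will be considered the baseline value".
- Fallback, for cases where the clock time of the dose and/or the observation is missing: "it is assumed that protocol planned in-office assessments obtained on the day of the first dose of study drug are prior to administration". Such values then count as baseline.

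The same section defines the term used in the fallback: "Study drug or study treatment refers to NKTR-255 or cetuximab".

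Protocol Table 1, footnote a, sets the general order of events: "All procedures and examinations should be performed before the administration of study drug(s) on dosing days, except as indicated". Footnote k is one of the indicated exceptions: "On C1D1 and C2D1, ECGs are required predose and end of NKTR-255 infusion". At every other timepoint the ECG is predose.

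SAP 7.6.5.2 and Table 6 depend on this baseline. They count new-onset QTcF bands, QTc increases of >30 to 60 ms and of >60 ms, and percentage changes in PR, QRS and heart rate. They also summarise the worst post-baseline change.

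**The concern.** The fallback assumes that planned assessments on the first-dose day came before the dose. For the C1D1 end-of-infusion ECG, the protocol makes that assumption false by design. The fallback does not consult the scheduled timepoint, which would separate the two C1D1 readings even without a clock time. If it applies, a reading taken under drug becomes part of the reference against which drug effect on the ECG is judged. QT/QTc prolongation is one of the SAP's own safety observation categories (SAP 7.6.2), so the affected table matters for safety.

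The anchor is also loose. The main rule refers to NKTR-255, while the fallback refers to the first dose of study drug. By the SAP's definition that could mean the cetuximab loading dose on Day -7.

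**Working it through.** The plan states no figure to reproduce. The check sets the rules side by side and follows a value through them.

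**Which day does the fallback cover?** If the first-dose day is Day -7, footnote k makes that ECG predose and the C1D1 end-of-infusion ECG is never reached. All Day -7 values precede NKTR-255 anyway, so on that reading the sentence does nothing for an NKTR-255 baseline. The sentence has an effect only if the day is C1D1, and then it covers the end-of-infusion ECG.

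**Inputs.** From the documents: one predose and one end-of-infusion ECG on C1D1, and the 30, 60 and 450 ms limits in SAP Table 6. Assumed, because the documents contain no QTc data: a predose value P = 430 ms and an acute shift d.

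**Formula.** With k untimed predose records and one untimed end-of-infusion record, baseline = P + d/(k+1). A later ECG at P + d, for example at the C2D1 end of infusion, is scored as d × k/(k+1). With k = 1 this is d/2.

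| True shift d (ms) | Averaged baseline (ms) | Scored change (ms) | Category with predose baseline | Category as scored |
|---|---|---|---|---|
| 31 | 445.5 | 15.5 | >30 to 60 | none |
| 40 | 450 | 20 | >30 to 60 | none |
| 60 | 460 | 30 | >30 to 60 | none |
| 61 | 460.5 | 30.5 | >60 | >30 to 60 |
| 100 | 480 | 50 | >60 | >30 to 60 |
| 121 | 490.5 | 60.5 | >60 | >60 |

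**Shift that must be exceeded to register >30 ms and >60 ms**, from threshold × (k+1)/k:
- k = 1: 60 and 120 ms
- k = 2: 45 and 90 ms
- k = 3: 40 and 80 ms

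**Other patterns, with k = 1:**
- Same direction, unequal size: d = +40 raises baseline by 20. A later +65 is scored 65 − 20 = 45 ms and moves from >60 to >30–60 ms.
- Opposite direction: d = −20 lowers baseline by 10. A later +55 is scored 55 + 10 = 65 ms and moves up from >30–60 to >60 ms.
- Rise confined to the C1D1 end of infusion: that reading is now baseline, so it is no longer a post-baseline value at all.
- New onset in a man: with P = 430 and d = 60, baseline is 460 ms. A later 470 ms counts as new onset in the >450–480 ms band against 430, but as already present against 460.

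**A second trigger.** Because the condition reads and/or, a missing dosing time alone invokes the predose assumption even when the ECGs are timed. Averaging of untimed values would not then apply, and the text does not say which C1D1 reading is baseline.

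**The case against.** The strongest reply is that this is only a fallback. If times are recorded, the main rule excludes the end-of-infusion ECG, and nothing in the documents says times are missing. The infusion-reaction rule in SAP 7.6.2 counts events within 48 hours of the start of NKTR-255 and allows only for a missing event onset time, which suggests that dosing times are recorded. This stands: how often the fallback would apply is unknown, and no bias has been shown.

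A second reply is that the fallback merely mirrors footnote a, so a sensible programmer would leave out an ECG planned for the end of infusion. That is a fair guess at intent, but the SAP does not carry over the exception.

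A reader might infer more than the documents support:

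- That contamination always shrinks the effect. It does not: the −20/+55 ms case inflates it.
- That vital-sign and laboratory analyses are generally affected. SAP Table 5 judges vital signs against absolute limits, and no post-dose safety laboratory draw on C1D1 is shown. The demonstrated case is the ECG.
- That the study-drug wording is a second harm. The Day -7 reading would not reach the C1D1 ECG, so the wording is an ambiguity to settle.
- That a QTc signal would be concealed. An ECG listing is planned (heading of SAP 7.6.6), clinically significant ECGs are reported as adverse events (Protocol 5.13.5 and 7.15), and QT/QTc events are summarised separately. None of these uses the derived baseline.

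**Conclusion.** The point holds as a conditional defect in a stated rule. For records without times, and with the first-dose day read as C1D1, the fallback admits a planned post-dose ECG to baseline. It then distorts the change-from-baseline and new-onset categories of SAP 7.6.5.2 and Table 6. With one reading of each kind, a later shift of equal size is scored at half. The direction of the distortion depends on whether later changes go the same way as the acute shift. The millisecond examples rest on assumed QTc values. The importance is low: the rule may never be triggered, and ECG listings and adverse event reporting would still show the readings. It is worth correcting because the wording gives a wrong baseline in the case it was written for.

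**What to change.** Amend the Baseline definition in SAP 6.6 in three ways:

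1. Limit the predose assumption, and the averaging of same-day values, to assessments whose scheduled timepoint is predose.
2. State that an assessment scheduled at or after the start of the first NKTR-255 infusion is never baseline, whether or not its clock time is recorded.
3. In the fallback, name the first dose of NKTR-255 in place of study drug, to match the main rule.

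The cost is a sentence or two of SAP text. The protocol schedule already defines the timepoints and no new data are needed, provided ECG records carry their scheduled timepoint. The documents do not show the case report form, so this should be confirmed when the text is changed.

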### **5.2.7 Survival Follow-up**

Following discontinuation of study treatment, patients will be contacted approximately every 3 months  $\pm 14$  days after the EOT by clinic visit or telephone, or other alternate methods such as email, contact with family, or public records (if allowed per local regulations), to obtain the information about alternative anti-cancer therapy and assess survival information until the patient meets the criteria for study discontinuation in Section [5.2.3.3](#).

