**Table 3: PFS Censoring Rules**

Situation	Date of Disease Progression or Censoring	Outcome
No post-baseline tumor assessments and no death	first dose date of Cetuximab	Censored
No progression and no death, and no new anti-cancer therapy started	Date of last assessment showing no evidence of disease progression	Censored
New anti-cancer therapy started without progression before	Date of last assessment before the start of anti-cancer therapy showing no evidence of disease progression	Censored
Disease progression reported on one or multiple response assessments without new anti-cancer therapy before	Date of earliest evidence of PD	Progressed
Death without PD or new anti-cancer therapy before	Date of death	Death
Two or more consecutive missing tumor assessments, and no progression before the missing assessment	Date of the last assessment prior to the missing assessment showing no evidence of disease progression	Censored

**Overall Survival (OS):** OS is defined as the time from the first dose date of Cetuximab to death from any cause. Patients will be followed until their date of death, loss to follow-up, or withdrawal of consent for further follow-up for survival, regardless of the start of anti-cancer therapy. Patients who are lost to follow-up will be censored at their last date known to be alive. Patients who do not have date of death at data cut-off date will be censored at their last date known to be alive. Patients who do not have any follow-up since first dose date of Cetuximab will be censored on the first dose date of Cetuximab.

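### The closing sentence of the SAP's last-known-alive definition contradicts its own list of sources; if programmed literally, it would bias Kaplan-Meier overall survival downward

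*SAP*

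**What the plan says.** SAP 6.6 (Last known alive date) gives a bulleted list of sources. Some are examinations: blood draws, vital signs, ECG, performance status, tumor assessments. Others need not be: "Start and end dates of anti-cancer therapies administered after study treatment discontinuation", adverse event dates, concomitant medication dates, the study discontinuation date, and "Last date of contact collected on the 'Survival follow-up' eCRF". The last of these carries a condition that the survival assessment date counts only if the status is alive.

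Two sentences follow the list. The first is "Only dates associated with actual examinations of the patient will be used in the derivation". The second is "Dates associated with a technical operation unrelated to patient status such as the date a blood sample was processed will not be used".

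Protocol 5.2.7 has patients contacted about every 3 months after end of treatment, "by clinic visit or telephone, or other alternate methods such as email, contact with family, or public records".

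The date feeds OS. In SAP 6.6.1, OS runs from the first cetuximab dose to death from any cause, and "Patients who do not have date of death at data cut-off date will be censored at their last date known to be alive". SAP 7.5.4 reports Kaplan-Meier OS at 6, 9 and 12 months with quartiles.

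**The concern.** The first closing sentence comes after the list, begins with a restriction and governs the whole derivation, so it reads as a filter on the list. A telephone call, an email or a records search is not an examination. A programmer who applies the filter drops those dates; one who works from the bullets keeps them. The SAP therefore permits two different OS curves from the same data.

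The filter is not neutral. Suppose one patient was last examined at month 5 and is confirmed alive by telephone at month 15, and another dies at month 15. Under the literal rule the first leaves the risk set at month 5 and the second stays in it to month 15. Whether a patient is censored early then depends on whether the patient has died.

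SAP 6.4 adds a second route in the same direction. A completely missing death date with a known reason for death is set to the last known alive date, so an examination-only date would move such a death earlier.

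**Working it through.** **Nothing to reproduce.** The documents give no OS assumption, power or sample size that rests on this rule. The check concerns direction and size only.

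**Direction.** The Kaplan-Meier estimate is S(t) = Π(1 − dᵢ/nᵢ) over death times up to t. The two readings have the same deaths dᵢ. The literal reading only moves censoring times earlier, so each nᵢ is the same or smaller and each factor is the same or smaller. S(t) under the literal reading can therefore never exceed S(t) under the list reading.

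**Size, by simulation.**

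Inputs from the documents:
- survival contact every 3 months from end of treatment (Protocol 5.2.7 and Table 1)
- last scheduled safety visit 60 days after the last dose (Protocol 5.2.6)
- censoring at the last date known alive (SAP 6.6.1)
- about 30 patients planned in Phase 1b (Protocol synopsis)

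Assumptions, not in the documents:
- exponential OS with true median 6, 9 or 12 months
- exponential time to end of treatment, mean 2 or 4 months, independent of death
- cut-off uniform at 6 to 24 months after entry
- all deaths before cut-off known, with their dates
- 50% or 100% of patients followed only remotely after the 60-day visit

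List reading: survivors are censored at the last 3-monthly contact. Literal reading: remotely followed survivors are censored at the last examination, taken as end of treatment plus 2 months. There were 400,000 simulated patients per row.

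| True median (months) | Mean time to end of treatment (months) | Remote share | True 12-month OS | List | Literal | List − literal | Median OS (months), list → literal |
|---|---|---|---|---|---|---|---|
| 6 | 2 | 50% | 0.250 | 0.232 | 0.182 | 0.050 | 5.93 → 5.58 |
| 6 | 4 | 50% | 0.250 | 0.236 | 0.195 | 0.041 | 5.97 → 5.74 |
| 9 | 2 | 50% | 0.397 | 0.377 | 0.298 | 0.079 | 8.69 → 7.62 |
| 9 | 4 | 50% | 0.397 | 0.379 | 0.318 | 0.061 | 8.73 → 7.94 |
| 12 | 2 | 50% | 0.500 | 0.481 | 0.388 | 0.093 | 11.40 → 9.38 |
| 12 | 4 | 50% | 0.500 | 0.483 | 0.413 | 0.070 | 11.47 → 9.90 |
| 6 | 2 | 100% | 0.250 | 0.232 | 0.121 | 0.111 | 5.94 → 5.28 |
| 6 | 4 | 100% | 0.250 | 0.234 | 0.145 | 0.089 | 5.96 → 5.52 |
| 9 | 2 | 100% | 0.397 | 0.377 | 0.186 | 0.191 | 8.67 → 6.64 |
| 9 | 4 | 100% | 0.397 | 0.380 | 0.234 | 0.146 | 8.76 → 7.27 |
| 12 | 2 | 100% | 0.500 | 0.482 | 0.233 | 0.249 | 11.44 → 7.61 |
| 12 | 4 | 100% | 0.500 | 0.484 | 0.300 | 0.184 | 11.51 → 8.55 |

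Reading the table:
- The loss in 12-month OS is 0.041 to 0.093 at 50% remote and 0.089 to 0.249 at 100% remote.
- The list reading falls short of the truth by only 0.014 (0.250 − 0.236) to 0.020 (0.397 − 0.377). That shortfall comes from the 3-month gap between contacts.

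**At the planned size.** In 3,000 replicates of 30 patients (mean time to end of treatment 3 months, 100% remote), the mean loss at 6 months was 0.042, 0.054 and 0.059 for true medians 6, 9 and 12. At 12 months it was 0.099, 0.167 and 0.217. The estimated median was never higher under the literal reading, as the argument above requires.

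**The case against.** The strongest reply is that the intended meaning is clear. The survival-contact bullet is specific and says how the date is to be used, which would be largely pointless if remote contacts were barred. The literal reading would also strip or weaken the bullets on later therapy, adverse events, concomitant medication and discontinuation. The sentence after it shows the contrast in mind: dates that reflect the patient's status against laboratory processing dates. SAP 6.4 speaks of an alive date drawn from several sources, and the OS definition refers to the date known alive, not to the last examination. A programmer working from the bullets would get OS right.

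Most of this stands. It makes the list reading the more likely intention, but it does not remove the instruction, and the visible text of the SAP's section on changes from the protocol does not settle the conflict.

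It does rule out a stronger reading that a reader might infer: that the plan excludes remote contacts and OS is therefore biased by the amounts above. The documents do not support that, because the same definition expressly admits those contacts. Nor can the 100% remote figures be taken as expected. Protocol 5.2.7 allows clinic visits, and Protocol 8.2 continues scans about every 9 weeks for patients who stop treatment without progression, until progression or new therapy. Those dates survive even the literal reading.

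It is also fair that little rests on OS. Only Phase 1b patients were enrolled, the primary endpoints are dose-limiting toxicities and treatment-emergent events, and no test or sample size uses OS.

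**Conclusion.** The contradiction is real; the bias is conditional. If the closing sentence is programmed over the bullets, Kaplan-Meier OS is biased downward. For assumed true medians of 6 to 12 months, 12-month OS is lower by roughly 0.04 to 0.09 with half of patients followed remotely and by roughly 0.09 to 0.25 with all of them, the latter an upper bound. If the listed contact dates are used, there is no material bias.

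The direction needs only that the deaths are the same under both readings. The sizes rest on the assumed survival, treatment duration, cut-off and remote share, and on complete capture of deaths. OS is secondary and descriptive, with no comparison, so no error rate or decision changes. It is still worth correcting: there is no control arm against which the error could cancel, and with about 30 patients, reported separately for HNSCC and CRC, a few wrongly censored survivors would move the curves.

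**What to change.** In SAP 6.6, delete the first closing sentence, or replace it with:

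*Only dates from the sources listed above on which the patient was examined or documented to be alive, including remote survival contact with status alive, will be used.*

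Keep the following sentence, which excludes dates of technical operations. The replacement should point back to the whole list. Wording that names only examinations and survival contacts would, read literally, drop the later-therapy, adverse event, concomitant medication, study treatment and discontinuation dates. The cost is one sentence in the SAP and a check that the derivation program matches it. No new data are needed.
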